In each CNC about 20 children are expected to suffer from moderate malnutrition.

The study hypothesis is that there will be no difference in improvement between intensive nutrition education group and less intensive education group in proportions improving from moderate malnutrition receiving nutrition education. The study will disprove the hypothesis if a 15% difference is detected with statistical significance.

$$\text{Using formula } n = \frac{p_1(1-p_1) + p_2(1-p_2)}{(p_1 - p_2)^2} (z_{\alpha} + z_{\beta})^2$$

(Reference: G W Snedecor and WG Cockran. Statistical Methods in Medical sciences. Oxford Publications 6th edition 1968, pp 111-114). Where p_1 is proportion of reduction of moderate malnutrition in intensive nutrition intervention group and p_2 is reduction in proportion of malnutrition in less intensive education group and $(z_{\alpha} + z_{\beta})$ is the function of level of significance and power of the statistical test.

$p_1=0.5$ and $p_2=0.35$

where z_{α} = level of significance at 5%, =1.96

and z_{β} = power of the study 90%, =1.28

where $(p_1 - p_2)$ = difference of proportion moving to mild malnutrition between control and intervention group.

$$n = \frac{0.5 \times 0.5 + 0.35 \times 0.65}{(0.15)^2} \times 10.5 = 222.$$

Taking a cluster effect of the design as the children will be selected from CNC s this is increased to $222 \times 1.5 = 333$. with a drop out possibility of 10%, it will be about 366 children in each group.

Total sample size will be $366 \times 2 = 732$ or 750 subjects.

Sample size for preventive study group:

Assumption is that mildly malnourished children will usually slip into moderate malnutrition without any nutrition education but with less intensive nutrition education, they will not slip into malnutrition. The study will be interested to detect a difference of 20% with a 5% probability and

90% power.

[figure not shown]
To detect this 20% difference the number of mildly malnourished children in two study groups will be $(121 \times 2) = 242$. The cluster effect of randomization by CNCs will be controlled by multiplying the number by a factor of 1.5 i.e. $242 \times 1.5 = 363$ for mildly malnourished groups and possible drop out (10%) can be covered with a total number of $(190 \times 2) = 380$ subjects.

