Data will be double entered in a microcomputer within a week of data collection. The field supervisors will visually check data before sending for entry into the computer. Any error, discrepancy or omission found during data entry will be reported to the investigators without delay. Data will be entered into microcomputer using SPSS Windows's program. Data on weight gain, frequency and introduction of complementary feeding will be compared between experimental groups. Complementary feed introduction and regularity will be compared among 6-9 month age groups in education and control groups. Comparability between intervention and control groups will be assessed by baseline characteristics such as age sex, nutritional status, socioeconomic characters, feeding practices, etc. Continuous variables will be assessed for normal distribution. T test will be performed to compare data of normal distribution; otherwise non-parametric test will be used. Chi-squared test will be performed for categorical variables, Multiple regression analysis will be done with weight gain as dependent variable and intervention and potential confounding variables such as age, sex, SES, baseline nutritional status, infection as independent variables. Separate analysis will be performed for periods of intervention, reinforcement and observation.

Compliance of nutrition education will be measured at 2 weekly observation period (already mentioned). Compliance will be measured as process indicator. Comparison of compliance will only

be done at the end of the study so that the investigators will have no idea about which group is more a less compliant. Therefore, these will be little change of introduction of bias due to non-compliance, effect of intensive or less intensive nutrition education will be compared as a whole. So complain will be seen as a factor of nutrition education with given intensive. Analysis of compliance data will be done by relating to the outcome effect of nutritional status and can be compared between two education groups.

Analysis of qualitative data

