The very most important behavioral change for children of this age would seem to be timely introduction of complementary food. It would be good to know before and after the intervention, what proportion of infants are receiving complementary food at 6 months, 7-9 months, 9-12 months, and over 12 months.

To make sure we don't duplicate BINP work already done, you should be sure to look carefully at the pre-BINP formative research carried out on behaviors. (You can get from [name]). It's quite thorough as to constraints and resistance points.

4. In the study as presently designed, you look carefully at two of the determinants of malnutrition (caring practices and morbidity) but not at food security information, i.e. economic status. Let me suggest that we profile right at the outset all the moderates by economic status (using the groupings already on the registration form (at least in Phase 2 thanas), and also by gender, and that we organize our results, accordingly by economic status and gender. In terms of the former, this would allow us to ask the question of whether the moderates from poor families will benefit as much from this intervention as moderates from households economically better off.¹
5. Why use mildly malnourished kids as a control group, when it would be perfectly ethical to use moderates in other areas experiencing the normal BINP intervention? Using "milds" as a control group would certainly bias the results, yes?
6. You seem to want to introduce different systems to deal with morbidity. Why not leave everything except the behavioral change the same as BINP so that results will be fully applicable?

Minor Points

Page 7 - Your discussion under food security seems to apply more to caring practices.

Page 12 (middle) - UNICEF is now suggesting that reaching a child before age 1 is yet better.

Page 16 - Note my comments #1 and 2 above.

Page 17 - Second full sentence: I've never seen such evidence.

How do you explain the 30% reduction in the control group?

Last full sentence: It would be useful to indicate more about the data used to assess complimentary feeding frequency. A recent BRAC study found that time constrained women rarely have the time to provide as many daily feedings as BINP suggests, particularly if this requires even one more cooking operation per day.

Page 18 (last four lines) - It would be useful to know how this compares and how it differs from what BRAC does now - another reason for doing the research together.

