f. What training is necessary for CNPs?

The study protocol has provision to work out this in details with implementing NGO at a stage when project has established smooth operation.

Duplication of BINP work has been avoided. The formative research already done has been considered during development of this project.

4. What is the differential impact of this approach on children from lower or better socioeconomic status?

The study will have a cross section of all children and impact will be analyzed by socioeconomic strata. Earlier study has shown no significant impact of economic status except very exceptionally poor and disadvantaged house holds. It will be considered with other confounding variable of growth as food security, disease control and caring practice all are considered together for growth performance.

5. Why use mildly malnourished children as controls?

Mildly malnourished children will be in education and no education to see the preventive effect of the nutrition education. They will match as perfect control for comparison. They will not be compared with moderately malnourished group.

6. Why introduce different system to deal with morbidity?

No additional efforts will be made for morbidity control as suggested by reviewer. Referral system is yet to take a momentum to address morbidity in BINP beneficiaries.

Minor points:

These have been addressed as suggested.

INSTITUTE OF NUTRITION, MAHIDOL UNIVERSITY

[name]

[contact] to 9 [contact]

Fax Cover Sheet

URGENT

DATE: ~~29 July 1999~~ | October 1999

TO: [name] [contact] [contact]
28D DR, B DHAKA, BANGLADESH [name]

FROM: [name] [contact]
[name]
[name]

RE: Proposal Review

Number of pages including cover sheet: 5

Message Dear [name] : As you've requested AGA?
Any questions, please E-mail me.
Best Regards,
[name]

BINP/OPRP PROPOSAL EVALUATION SCORING FORM (1)

TH

1002

2/5

BINP/OPRP PROPOSAL EVALUATION SCORING FORM (1)

Please score on a 1-5 scale: 1 = very bad - 5 = very good

Project Proposal Title "Feasible means to address moderately malnourished children within BINP communities" by [name] et al.

		SCORE
1	Background	3
2	Description of objectives	2
3	Description of hypotheses or conceptual framework	3
4a	Design: Definitions of key concepts and variables	3
4b	Design: Sample size and sampling strategy	4
4c	Design: Clarity of analysis plan	3
4d	Design: Feasibility of proposed methods	3

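### Whether impact differs by socioeconomic status is to be answered within strata, with SES otherwise only a confounder; no stated analysis compares effects between strata

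*Protocol*

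**What the plan says.** An external peer reviewer (Reviewer I, major suggestion 4) asked "whether the moderates from poor families will benefit as much from this intervention as moderates from households economically better off". In the Response to reviewer's comments, Reviewer-1, item 4, the investigators restate this as "What is the differential impact of this approach on children from lower or better socioeconomic status" and answer: "The study will have a cross section of all children and impact will be analyzed by socioeconomic strata". The same answer adds that economic status will be handled together with other confounders of growth.

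The Data Analysis section names t tests or non-parametric tests for continuous data, and "Chi-squared test will be performed for categorical variables". It gives one model, a multiple regression on weight gain with "intervention and potential confounding variables such as age, sex, SES, baseline nutritional status, infection as independent variables". No term for intervention by SES is named there.

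The sample size for the management study serves the overall INE v LINE contrast only, and that contrast is decided by a significance test: "The study will disprove the hypothesis if a 15% difference is detected with statistical significance". The protocol gives no number of SES strata and no cut-points.

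**The concern.** Whether an intervention helps poor and better-off families equally is a question about the difference between two effects. The stated tools do not estimate that difference. An SES main effect adjusts the overall comparison for SES. An analysis inside each stratum gives separate effects. Neither sets one effect against another.

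The risk lies in how stratum results would be read. The sample is sized for the whole group, so each stratum has much less power. A significant result in one stratum and a non-significant one in another can then arise when the true effect is the same in both. Read as a finding, this would say that the extra sessions of INE pay off for some households and not for others. The dissemination plan expects the national nutrition programme to take up the results at once, so such a reading could affect how intensive education is targeted.

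**Working it through.** **Inputs.** From Sample size for management study group: 0.50 (INE) v 0.35 (LINE), two-sided 5% (1.96), 90% power, cluster factor 1.5, 10% dropout. From Selection and randomization procedure: 375 children and 20 CNCs per arm, with whole CNCs allocated. Assumed, because not stated: 2, 3 or 4 equal strata, the same true effect in each, and a separate test in each.

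**1. The plan's own figure.** (0.50×0.50 + 0.35×0.65)/0.15² × 10.5 = 0.4775/0.0225 × 10.5 = 222.8 (plan: 222). 222 × 1.5 = 333, and 333 × 1.1 = 366.3 (plan: 366). With 333 evaluable per arm, effective n = 333/1.5 = 222, SE = √(0.4775/222) = 0.046, and power = Φ(0.15/0.046 − 1.96) = 90%. The plan's figure is reproduced.

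**2. Power per stratum.** With s strata, n = 333/s per arm, SE = √(0.4775 × DEFF/n) and power P = Φ(0.15/SE − 1.96). Two design effects (DEFF) are used. One is 1.5 throughout. The other is a smaller value, because each stratum has fewer children per CNC: the intracluster correlation (ICC) implied by the plan is 0.5/(18.75 − 1) = 0.028, and DEFF = 1 + 0.028 × (m − 1) with m = 333/(20s).

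**3. Chance that strata disagree on significance.** Treating strata as independent, this is 1 − Pˢ − (1−P)ˢ. For two strata at DEFF 1.5: 1 − 0.628² − 0.372² = 47%.

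**4. Strata that share CNCs.** If each stratum is spread evenly over the CNCs, stratum estimates correlate at ρ = ICC × m/(1 + ICC × (m − 1)). For two strata, m = 8.3 and ρ = 0.23/1.21 = 0.19. For three and four strata, ρ = 0.14 and 0.11. The last column repeats step 3 with the smaller DEFF, using a multivariate normal distribution with this correlation.

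| Strata | Power, DEFF 1.5 | Power, smaller DEFF | Disagree, DEFF 1.5 | Disagree, smaller DEFF | Disagree, smaller DEFF and ρ |
|---|---|---|---|---|---|
| 2 | 63% | 72% (DEFF 1.21) | 47% | 40% | 36% |
| 3 | 46% | 58% (1.13) | 75% | 73% | 67% |
| 4 | 37% | 48% (1.09) | 82% | 87% | 82% |

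A simulation of 200,000 trials with independent strata and 225 effective per arm (375 × 0.9/1.5) gave 47%, 75% and 81%. On the same 225, two unequal strata disagree in 52% (33/67 split) to 63% (20/80) of trials. A true difference of 10 points in place of 15 gives 44%, 53% and 56% for two, three and four strata.

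**5. No INE-LINE difference.** The chance of at least one significant stratum is 1 − 0.95ˢ = 9.8%, 14.3% and 18.5%. The correlation in step 4 lowers these only to 9.6%, 14.1% and 18.4%.

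**6. The interaction test.** Under a common effect it signals a difference in 5% of trials by construction. With two equal strata at DEFF 1.5, the stratum SE is 0.0656 and the SE of the difference between effects is 0.0656 × √2 = 0.093. Keeping the same variance, power for 15 points in one stratum and 0 in the other is Φ(0.15/0.093 − 1.96) = 37%. A gap of 2.80 × 0.093 = 26 points is needed for 80% power. With the smaller DEFF and shared CNCs, SE = 0.0588 × √(2 × (1 − 0.19)) = 0.075, and the same calculation gives about 52% power and a gap of 21 points.

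**The case against.** The strongest reply is that the faulty step is inferred. Analysing impact by strata fits estimates with intervals, or an interaction model, as well as separate tests, and nothing says that stratum p-values will be set against each other. This stands, so every figure above is conditional on separate testing.

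Second, interaction tests, multiplicity rules and exploratory labels are often left to a statistical analysis plan, which may exist. This stands for the details. It does not remove the point: the protocol itself names a differential question, names a method, and gives SES the role of confounder. That combination does not answer the question, and a plan written faithfully from it would not either.

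Third, the undertaking sits in a reply to peer review and not in the hypotheses, objectives or Data Analysis. Such replies do not always match the main text: one says cost-effectiveness is not a direct objective, while the Specific Aims list it. This lowers the weight of the point, but the sentence is a current undertaking and the main text does not withdraw it.

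A reader might infer that strata would usually disagree, or that a false differential effect is likely. The documents do not support that. The restated question has two levels, lower and better, and with two equal strata the figure is below half. Disagreement in significance also becomes a false finding only if someone reads it as one.

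A reader might also infer that the trial could wrongly conclude that education works only for some households. Both management arms receive education, so the contrast is one of intensity. If the reply's reference to the approach means improvement with education in general, or if weight gain is the outcome, these powers do not apply.

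**Conclusion.** The point holds as a minor one. The protocol poses a question about a difference between effects, and none of its stated analyses compares effects between SES strata. If strata were tested separately and the planned 15-point effect held in each, significance would differ between strata in roughly 36-47% of trials with two equal strata and in about two-thirds or more with three or four. With no INE-LINE difference, at least one stratum would be significant in about 10-19%. The ranges reflect the design effect assumed within strata, the correlation of strata that share CNCs and, under no difference, the number of strata. That number is an assumption throughout. Even the low end for two strata is well above the 5% rate of a false differential effect that an interaction test would give. The overall INE v LINE comparison is not affected.

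**What to change.** In Data Analysis, and in the answer to Reviewer-1 item 4, state that the differential-impact question will be answered by one arm-by-SES interaction term in the model for the main endpoint, with allowance for clustering by CNC. Say how SES is grouped. Report stratum estimates with confidence intervals, label the analysis exploratory, and state that significance within a stratum will not be used to claim a differential effect.

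The cost is one model term and a few sentences. SES is already collected in the planned baseline survey, so no new data are needed. The downside is low power: about 37% for 15 points v 0 with two equal strata at DEFF 1.5, and about half if the strata share CNCs. The likely result is an interval for the difference between strata, not a verdict.

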The Bangladesh Integrated Nutrition Project (BINP) of the Government of Bangladesh has started showing reduction in malnutrition of women and children under two years of age in last 3 years of it's activities. Moderately malnourished children form a large proportion of children in the community. With success of the BINP this proportion is farther increasing as severely malnourished children are improving and "graduating" to the moderately malnourished category. Recent operations research of BINP shows that it is possible to reduce moderate malnutrition substantially through a specific package of intensive nutrition education. (INE). That was a demonstration study to test the efficacy of the approach on a relatively small number of children with intensive intervention. There is now an urgent need to define an effective and feasible means applicable in a larger population in the country. A study will be therefore conducted in 4 division of BINP thanas of Bangladesh over an 18-month period. Moderately malnourished children will be in management intervention and mildly malnourished and well-nourished infants will be in preventive intervention group. For management intervention, a total of 750 moderately malnourished will be randomized to receive either intensive nutrition education or less intensive education. For preventive purpose, 380 mildly malnourished children of 6 months to 2 years of age and 100 well nourished infants of 6 to 9 months of age will receive either less intensive education or no education. Infants between 6 to 9 month ages will be brought under less INE to ensure their complementary feeding practice. Care givers of one group of mildly malnourished children and one group of 6-9 month old infants will not receive any education to serve as controls. Focus Group Discussion (FGD) based INE will be conducted taking into consideration of geographical variation for an in-depth understanding of culture. Focus group discussion will be held with mothers to discuss beliefs, food habits and feeding practices of these children. An anthropologist and a nutritionist will jointly develop the nutrition education package. INE on child caring and on food security and disease control. Mothers of the first intervention group will receive intensive nutrition education and motivation for childcare, complementary food demonstration, and household food mobilization for child feeding twice weekly for first three months, which will be then reinforced once in a week for the last three months of intervention. The less intensive intervention group will receive nutrition education with the same components twice a week for the first month then once a week for two months and then twice monthly for the last three months of intervention. INE will be given for a total of 6 months. An observation will be done to identify for sustainability effect for an additional period of 6 months. Their weight and length gain will be recorded. The Community Nutrition Promoter (CNP), Community Nutrition Organizer (CNO), women's group and village nutrition committee will be involved in motivating and

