
Conceptual frame work

Research Design and Methods

Describe in detail the methods and procedures that will be used to accomplish the objectives and specific aims of the project. Discuss the alternative methods that are available and justify the use of the method proposed in the study. Justify the scientific validity of the methodological approach (biomedical, social, or environmental) as an investigation tool to achieve the specific aims. Discuss the limitations and difficulties of the proposed procedures and sufficiently justify the use of them. Discuss the ethical issues related to biomedical and social research for employing special procedures, such as invasive procedures in sick children, use of isotopes or any other hazardous materials, or social questionnaires relating to individual privacy. Point out safety procedures to be observed for protection of individuals during any situations or materials that may be injurious to human health. The methodology section should be sufficiently descriptive to allow the reviewers to make valid and unambiguous assessment of the project. (DO NOT EXCEED TEN PAGES. USE CONTINUATION SHEETS).

Material and methods:

A two-prong nutrition intervention study will be conducted in four administrative divisions of Bangladesh. One strategy will include nutrition education for prevention of malnutrition and other will include nutrition education for management of moderate malnutrition in 6-24 months old children using UNICEF guidelines of food security, disease control and caring practices. The approach will include anthropological and nutrition skills to educate mothers on specific knowledge skills.

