FGD will be conducted on mothers in 6 groups each from 3 CNC's (1 control and 2 study areas). There will be 6-8 mothers of moderately malnourished children in each Focus Group Discussion. This is expected to be more or less homogenous, since mothers having young children in the villages are of similar age FGD will be conducted by the anthropologist. Moderator will play the role of guiding the group on the right topic by putting them on the track. The research personnel will facilitate discussion but they will not influence the discussion. A tape recorder will be used to record the discussion. One facilitator will take notes. Obtained data from FGD will be analyzed manually by using coding.

The FGD will be conducted again to evaluate the change in behaviour and the process indicators. The method indicated above will be followed in the later part of the study.

A pre-test on knowledge of child feeding practice will be done and will be repeated with same the questionnaire after the diet counselling sessions with the mothers. Data on feeding frequency, preparation of information on child feed, dietary ingredients, frequency of feeding and constraints will be recorded at two weekly intervals in study groups. Post test will be conducted at the end of

nutrition education period.

The health assistants will be pre-testing the nutrition knowledge of the mothers and mothers will be observed before actual training is given. These subjects will not be included into study. This will reduce observer bias of the health assistants.

Outcome variables:

1. Mothers understanding and ability to identify moderate malnutrition in children.
2. Mothers understanding on consequence of moderate malnutrition.
3. Change in knowledge of mothers in feeding practices.
4. Frequency of home feeding (Breast-feeding and supplementary feeding).
5. Frequency of seeking medical care during illness, referral, incidence, duration of illness.
6. Adequacy of child feeding, frequency & type of feeding.
7. Weight gain, weight for age and weight for height at the end of intervention.
8. Proportion of complementary feeds in 6-9 months age group.
9. Nutritional status of children at various phases of intervention and observation.
10. Adaptation level of nutrition education program by CNP, CNO.
11. Constant of not practicing education knowledge.

Secondary outcome variables: -

1. Incidence and prevalence of diarrhoea and ALRI
2. Referral success and failure
3. Resistance to education

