4. Food insecurity for child
5. Mothers time constraint for CF preparation
6. CNP time constraints for INE

Process indicators:

5. Number of counseling sessions
6. Proportion of attendance by mothers to counseling session
7. Proportion of attendance of supplementary feeding demonstration session
8. Number of home visits of by Health assistants
9. Use of IEC materials in sessions.
10. Number of community sessions with mothers groups, women's group, and VNMC.
11. Proportion weighing sessions.
12. Member of VNMC meetings.
13. Percent of feeding frequency change.
14. Record of referral.
15. Feeding related behaviour.

Quality control measures:

Quality assurance will include questionnaire development, FGD, intensive staff training, standardization of study procedures, which will be written in detailed manuals, regular staff meetings and supervision by the investigators. The project investigators in 15% random samples will directly supervise systematic data collection. Anthropometry will be standardized at the beginning of monthly sessions by trained nutritionist. External validation of anthropometry will also be done. Validation of nutrition education will be done by attending the sessions by supervisors during group with a check list education and with separate interview. Cross check with mothers for preparation of feeds and feeding frequency will be done by nutritionist. Feeding frequency will be rechecked after the day of interview in 15% of the randomly selected sessions at the household levels. Investigators will make random spot checks and will re-interview at least 15% of mothers on child morbidity on the same day using the same questionnaire. With identification of any discrepancy, the data will be informed to the respective health workers and corrections will be done by supervisor's assistance. Each child will have a record file of important events such as migration, referral, and death and will be kept with project office. The field activity will be communicated to PI by the project supervisors and senior staff by phone or fax in between the visits in the field. Data will be checked by running checking program in computer after collection and before analysis.

Adaptation process of the Community Nutrition Promoters (CNP's) and Community Nutrition Organizer (CNO's):

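### Food security, disease control and caring practice are called confounders, with no limit to values recorded before the education starts, although the education targets all three

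*Protocol*

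**What the plan says.** The first peer reviewer asked (major suggestion 4) "whether the moderates from poor families will benefit as much from this intervention as moderates from households economically better off". The reply to item 4 promises that "impact will be analyzed by socioeconomic strata". It then adds that economic status will be taken with "other confounding variable of growth as food security, disease control and caring practice all are considered together for growth performance". It gives no time of measurement and no model.

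The Data Analysis section plans a multiple regression of weight gain on intervention and "potential confounding variables such as age, sex, SES, baseline nutritional status, infection as independent variables". The list is open, and the word baseline is attached to nutritional status only.

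Elsewhere the same three factors are the content of the intervention. The Project Summary describes "INE on child caring and on food security and disease control", and Material and methods describes education "using UNICEF guidelines of food security, disease control and caring practices". The conceptual framework section equates food security in young infants with appropriate breast-feeding and timely complementary feeding. The outcome lists include "Adequacy of child feeding, frequency & type of feeding" (outcome 6) and "Food insecurity for child" (secondary outcome 4).

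**The concern.** A confounder of the education effect must not be a consequence of the education. CNCs are allocated at random, and the education aims to change feeding, care and response to illness. Values of these factors recorded during or after the education are therefore on the path from education to growth. The protocol's reply to item 3d sets out that path: education changes behaviour, and behaviour changes the child's nutrition.

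Poverty also acts partly through them. Annexure 3 describes extremely poor households as food insecure, and Annexure 4 reports that many poor families in the Shahrasti study managed one meal a day.

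A regression that holds follow-up values fixed asks how much the education helps among children whose feeding and care are the same. That pulls the adjusted INE–LINE or LINE–control difference in weight gain towards zero. In a study whose hypothesis is equal effectiveness, this is the direction that agrees with the hypothesis. It also shrinks any shortfall in poor families, which is what the peer reviewer wanted to see.

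**Working it through.** **1. The plan's own figure.** The documents give no figure for the economic-status comparison. The management sample size reproduces: (0.25 + 0.2275)/0.0225 × 10.5 = 222.8, given as 222; 222 × 1.5 = 333; 333 × 1.1 = 366. It is for two proportions, 0.50 and 0.35, with no covariates, so nothing below changes it.

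**2. Do the arms differ in exposure to these factors?** The session-frequency tables say so. Referral and disease control has 12 + 3 = 15 sessions under INE and 6 + 3 = 9 under LINE. The line for CP (read here as caring practice), breast-feeding and hygiene has 12 + 6 = 18 and 6 + 3 = 9.

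**3. When are the factors measured?**
- Before education: the survey covers income, household food status, parental education and occupation, and family size and type. Feeding practices are listed as a baseline characteristic in Data Analysis. Disease control is not among the survey topics.
- After education starts: feeding data every two weeks, and morbidity at two-weekly home visits.
- Infection, a named covariate, has no stated time.

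So both kinds of value will exist for feeding, while illness is recorded mainly during follow-up.

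**4. What each choice does.** All coefficients here are assumed. Let A = education, P = poor, F and C = food security and caring scores (0 = baseline, 1 = follow-up), and d = effect by any other route.
- F1 = F0 + A(0.6 − 0.3P) + error
- C1 = C0 + A(0.5 − 0.2P) + error
- Growth = d·A(1 − 0.5P) + 0.5·F1 + 0.4·C1 + error

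Total effect in better-off families: d + 0.5×0.6 + 0.4×0.5 = d + 0.50.
Education-by-poverty interaction: −0.5d − 0.5×0.3 − 0.4×0.2 = −0.5d − 0.23.
With F1 and C1 held fixed, what is left is d and −0.5d.
Mediated share in better-off families: f = 0.50/(d + 0.50).

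| d | f | Total effect / interaction | After adjusting for F1, C1 |
|---|---|---|---|
| 0 | 1 | 0.50 / −0.23 | 0 / 0 |
| 0.2 | 0.71 | 0.70 / −0.33 | 0.20 / −0.10 |
| 0.5 | 0.50 | 1.00 / −0.48 | 0.50 / −0.25 |

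A simulation of 400,000 children with these coefficients agrees: 0.50 / −0.22 to 0.00 / +0.01; 0.69 / −0.32 to 0.20 / −0.09; 0.99 / −0.48 to 0.50 / −0.25.

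Adjusting for F0 and C0 instead gave 0.50 / −0.22, 0.70 / −0.32 and 1.00 / −0.48, so the education effect and the interaction are unchanged. In that simulation F0 and C0 were set 0.8 and 0.3 lower in poor families. Baseline adjustment removes only the resulting main association of poverty with growth: −(0.5×0.8 + 0.4×0.3) = −0.52, to 0.00.

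**The case against.** The reply's firm promise is analysis by socioeconomic strata, which answers the peer reviewer's question with no adjustment for food security or care. The sentence at issue speaks of determinants of growth and specifies no model. The context points partly to baseline: the peer reviewer treats food security information as economic status and asks for it to be profiled at the outset, and a baseline survey of food status is planned. Data Analysis names neither food security nor caring practice. One factor may be a covariate at baseline and an outcome later, as nutritional status is here. Covariate timing is often left to the SAP.

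Most of this stands. A reader might infer that the plan definitely adjusts the education effect away. The documents do not support that, because neither timing nor model is stated. A reader might also infer that the planned 90% power falls with the mediated share. It does not: that power belongs to a comparison of proportions, and categorical variables are tested by chi-squared, which has no covariates. Nor is caring practice named in the outcome lists; only feeding adequacy and food insecurity are.

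What the objection does not remove is the label. The protocol calls confounders the factors that it makes the targets of education, its regression takes an open list of confounders, and the repeated data on feeding and illness come from after the start. That is a misstatement in this document, not a detail left for later. An analyst following it could reasonably enter follow-up values.

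**Conclusion.** The point holds as a clarification that should be made. It concerns the weight-gain regression and any adjusted answer to the economic-status question, for INE against LINE or LINE against control. The loss occurs only if values recorded after the start of education are entered, and only for the share that passes through them: none if that share is zero, half at f = 0.50, all at f = 1. The documents give no estimate of f.

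Total removal of the effect is therefore the extreme case, not the expected one. The illustration also assumes linear effects and no unmeasured common cause of follow-up feeding or care and growth. With such a cause, the adjusted coefficient would carry further bias of unknown direction. The unadjusted comparisons, the sample size and a stratified analysis on baseline economic status are sound on this point.

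**What to change.** - In the reply to item 4, drop the word confounding for these three factors. There and in the Data Analysis regression, state that only values recorded before education starts may be covariates, for example SES, household food status from the survey, and baseline feeding practices. Apply the same limit to infection.
- Answer the economic-status question by comparing arms within baseline socioeconomic strata, or by an arm-by-SES interaction, with allocation by CNC respected.
- Report follow-up food security, disease control and caring practice by arm as outcomes, adding caring practice to the list, or in a separate analysis labelled as mediation.

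The cost is wording. The baseline survey and baseline feeding data are already planned, and no extra children or visits are needed.
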